Femoral Triangle and Adductor Canal Blocks Versus Femoral Nerve Block for Total Knee Arthroplasty

NCT03645954

August 24, 2018

Study Protocol

Aim of the study: to evaluate and compare the femoral triangle and adductor canal blocks and the femoral nerve block regarding the, extent of motor blockade, postoperative analgesic efficacy, ability of early ambulation in patients following primary total knee arthroplasty.

Objectives:

- 1. To assess and compare the extent of motor blockade after the surgery between the femoral triangle and adductor canal blocks group and the femoral nerve block group after the primary total knee arthroplasty.
- 2. To compare postoperative pain control effects between the femoral triangle and adductor canal blocks group and the femoral nerve block group after the primary total knee arthroplasty.
- 3. To estimate the need for additional opioid analyses and their adverse effects in the femoral triangle and adductor canal blocks and the femoral nerve block groups of patients after primary total knee arthroplasty.
- 4. To compare patients postoperative satisfaction rates between the femoral triangle and adductor canal blocks group and the femoral nerve block group after the primary total knee arthroplasty.

Design and Methods:

The prospective, double-blinded study includes American Society of Anesthesiologists (ASA) physical status I-III in preoperative assessment, aged 18-90 years, scheduled for primary total knee replacement surgery. Preoperatively patients will be blindly randomized into one of two groups: the femoral triangle and

adductor canal blocks group and the femoral nerve block group. Group assignment will be concealed by opaque envelopes that will be opened only after the patients enrollment. The anesthesiologist who will perform the block will be aware of the treatment, but the participant and outcomes assessor will be blinded to the group assignment. All blocks will be performed by the anesthesiologist under the ultrasound guidance. The femoral nerve block will be performed with 20 mL of 0.125% bupivacaine injection. The femoral triangle and adductor canal blocks will be performed together with injection of 10 mL of 0.125% bupivacaine for each block. During the perioperative period all patients will receive premedication of midazolam 2.5-5 mg and dexamethasone 4 mg. A slow fluid infusion of crystalloids with 1 g of tranexamic acid and 10 mg of ketamine will be started once as an intravenous cannula will be placed. Spinal anesthesia after identification of the subarachnoid space will be performed with 15 mg of levobupivacaine. After that, one of the peripheral nerve blocks will be performed. During surgery patients will be sedated with intravenous propofol. The local infiltration analgesia will be performed by the surgeon at the end of surgery with combination of 30 mL of 0.5% bupivacaine, 0.3 mL of 0.1% adrenaline and 90 mL of 0.9% sodium chloride. After the surgery patients will be transferred to the post-anesthesia care unit (PACU). After the surgery for analgesia NSAIDs will be available to both groups of patients. NSAIDs such as dexketoprofen 50 mg will be administered 2 times and acetaminophen 1 g will be administered 3 times per day. Opioids will also be available to patients as intramuscular boluses of pethidine 50 mg or morphine 10 mg without restriction and administered for moderate or severe pain. The extent of motor blockade will be evaluated at 3, 6, 24, 48 hours after surgery. Patients will be asked to flex the foot, to flex the knee and to lift up the straight leg. The possible leg motion at 3, 6, 24 and 48 hours postoperatively will be assessed with Bromage scale grades. Postoperative pain control efficacy will be assessed at 3, 6, 24 and 48 hours after surgery using visual analogue scale (VAS) from 0 to 10 (0 - no pain, 10 - worst imaginable pain) at rest, during active and passive 45 degree knee flexion. The requirement of additional analgesics and their adverse effects will be recorded.

Patients ability of early ambulation will be evaluated using Timed Up and Go (TUG) test at 24 and 48 hours after surgery. To do the TUG test, patients will have to sit down on the bed, get up from the bed, walk 3 meters forward, turn, walk back 3 meters to the bed and sit down. The time taken by a patient to perform this test will be calculated with a chronometer. After the conversation with each patient and assessment of postoperative pain control efficacy, extent of motor blockade, ability of early ambulation, the rate of patient satisfaction will be evaluated using a 10 point scale from 0 to 10 at 3, 6, 24, 48 hours after surgery. The rate of complications (if any), including falls, local anesthetic toxicity or neurological complications, will be recorded in both groups of patients. According to study protocol, both groups of patients will be compared in terms of the extent of motor blockade postoperative pain control, ability of early ambulation, need for additional opioid analgesics, satisfaction rates over the time of clinical recovery.

Statistical Analysis Plan

The age, gender, BMI, ASA status will be collected.

The variable for power calculation analysis is the difference in motor blockade between the groups of patients. The difference in motor blockade of 30% would be clinically significant. To detect differences for a power of 90% and a 2-tailed α error of 0.05, a sample size of 33 patients per group would be required. However, due to possible missing data, 80 patients will be included in the study.

The statistical analysis will be performed using SPSS (version 25.0 IBM). The Kolmogorov-Smirnov test will be used to assess the normality of data distribution. For normally distributed numerical variables the Student t test will be used to compare means. Categorical variables will be compared using the Chi-squared test. A p value < 0.05 will be chosen as statistically significant.

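### Opioid adverse effects are recorded as effects of the analgesics given, with no scheduled question to all patients and no denominator, so the result by arm is open to bias if opioid use differs

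*Combined protocol and SAP*

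**What the plan says.** Objectives, item 3, reads "To estimate the need for additional opioid analyses and their adverse effects", for both named groups (the word after opioid is evidently meant to be analgesics). Design and Methods gives the matching collection rule: "The requirement of additional analgesics and their adverse effects will be recorded". In both places the adverse effects belong grammatically to the additional analgesics.

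Opioids are available to both arms under one rule, "without restriction and administered for moderate or severe pain". Motor block, pain and satisfaction each have fixed assessments at 3, 6, 24 and 48 h. Adverse effects have no time points, symptom list, attribution rule or denominator.

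The closing list of between-arm comparisons in Design and Methods ends with "need for additional opioid analgesics, satisfaction rates over the time of clinical recovery". Opioid need is on that list and opioid adverse effects are not. A separate safety record is planned: "The rate of complications (if any), including falls, local anesthetic toxicity or neurological complications, will be recorded in both groups of patients". The Statistical Analysis Plan adds only a general rule: "Categorical variables will be compared using the Chi-squared test".

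**The concern.** Two features of the design make an attribution-based record fragile.

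First, opioids are triggered by postoperative pain, which objective 2 expects the blocks may change. Whether a patient receives an opioid is therefore a consequence of randomisation, and the trial itself plans to compare it between arms.

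Second, every patient also receives midazolam, ketamine, a spinal anaesthetic and propofol. Nausea, dizziness or sedation in the first hours has several possible causes. The same symptom may be labelled an opioid effect in a patient who had pethidine or morphine and go unrecorded in one who did not.

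If opioid use differs, the arm with more users offers more chances for background symptoms to be counted. If rates are instead calculated among recipients, a real reduction in events that comes from fewer patients needing opioids disappears. At stake is the adverse-effect half of objective 3. The sample size rests on motor blockade and is not affected.

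**Working it through.** **Inputs from the documents.** Recording is tied to the analgesic given; opioids are given on a post-randomisation trigger; 80 patients are to be included in two groups. The documents give no rate for opioid use, opioid effects or background symptoms, so there is no figure to reproduce.

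**Assumed inputs.**
- u1, u2: share of each arm that receives an opioid.
- e = 0.30: probability of an opioid-caused symptom in a recipient.
- b = 0 to 0.30: probability of a background symptom, the same in both arms and independent of the opioid effect.

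The block is assumed to act on these symptoms only through opioid use.

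**Formulas, per randomised patient in an arm with use u.**
- Opioid-caused events: u × e. Arm difference: e(u1 − u2).
- Symptoms counted in users only, all attributed to the opioid: u[1 − (1 − b)(1 − e)].
- Symptoms asked of everyone, any cause: u[1 − (1 − b)(1 − e)] + (1 − u)b. Arm difference: e(1 − b)(u1 − u2).
- Excess of users-only capture over the opioid-caused difference: b(1 − e)(u1 − u2).

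**Use 60% v 40%.** The opioid-caused rates are 0.6 × 30% = 18% and 0.4 × 30% = 12%, a difference of 6.0 points.

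| b | Users only | Difference | Excess over 6.0 | Asked of all | Difference |
|---|---|---|---|---|---|
| 0 | 18.0% v 12.0% | 6.0 | 0 | 18.0% v 12.0% | 6.0 |
| 0.10 | 22.2% v 14.8% | 7.4 | 1.4 | 26.2% v 20.8% | 5.4 |
| 0.20 | 26.4% v 17.6% | 8.8 | 2.8 | 34.4% v 29.6% | 4.8 |
| 0.30 | 30.6% v 20.4% | 10.2 | 4.2 | 42.6% v 38.4% | 4.2 |

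Check at b = 0.20: 1 − 0.8 × 0.7 = 0.44; 0.6 × 0.44 = 26.4%; 0.4 × 0.44 = 17.6%; excess 0.20 × 0.70 × 0.20 = 2.8 points.

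**Other cases.**
- Equal use (50% v 50%): both rules give a difference of 0 at every b.
- Use 70% v 30%, b = 0.20: users only 17.6 points, asked of all 9.6, opioid-caused 12.0, so the excess is 5.6.
- No opioid effect (e = 0), b = 0.20, use 60% v 40%: users only gives 0.6 × 20% = 12% v 0.4 × 20% = 8%, when opioid-caused events are 0% v 0%.
- Per-recipient denominator, b = 0: 30% v 30%, which hides the 18% v 12% seen over all randomised patients.

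The excess assumes that every background symptom in a user is put down to the opioid. If only a share is, it shrinks in proportion. With 40 patients per arm (equal allocation assumed), 1.4 to 4.2 points is 40 × 0.014 = 0.6 to 40 × 0.042 = 1.7 patients.

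**The case against.** A reader might infer that adverse effects are recorded only in opioid users and that the comparison between arms is therefore biased. The documents do not support that.

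- They are silent on patients without opioids and do not say that their symptoms are ignored. The complications record covers both groups whatever they received, and its examples are not exhaustive. Every patient is also spoken to at the four assessments.
- A patient given no opioid cannot have an opioid adverse effect, so zero is the correct value. With all randomised patients as denominator and accurate attribution, the arm difference is a valid downstream effect of the block. Bias needs unequal use together with misattribution, or a per-recipient denominator, and the plan specifies none of these.
- Objective 3 says estimate where the other objectives say compare, and no formal comparison of adverse effects is listed.
- Under the masking rule, "the participant and outcomes assessor will be blinded to the group assignment".

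Most of this stands, and it limits the point to a risk. Three parts carry less weight. Masking covers the allocated group and not receipt of an opioid, so it does not stop nausea being labelled an opioid effect because an opioid was given. The complications record names no opioid-type symptom. Estimating a rate in each of two randomised arms invites comparison, and each estimate depends on the same attribution.

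**Conclusion.** The point holds as a risk that the plan leaves open. The recording rule depends on receipt and attribution, both of which follow randomisation, and neither a schedule nor a denominator is fixed. In the model, distortion is zero if opioid use is equal, if there are no background symptoms, or if attribution is perfect and all randomised patients are counted. Otherwise, for an assumed 60% v 40% use, 30% opioid effect and 10% to 30% background, it inflates a 6.0-point difference by 1.4 to 4.2 points, fewer than two patients per arm. Its direction follows the arm with more opioid use, and the documents give no figure for that. All rates are assumed and the endpoint is not the one used for the sample size. The change is worth making because it is cheap and because symptoms not asked about at the time cannot be reliably recovered later.

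**What to change.** Replace the recording sentence in Design and Methods with a rule to this effect: at 3, 6, 24 and 48 h the blinded assessor asks every randomised patient, whether or not an opioid was given, about a fixed list of symptoms (for example nausea, vomiting, itching, sedation, dizziness and urinary retention) and records each as present or absent since the last assessment, without judging cause.

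In the analysis, report by arm the proportion of all randomised patients with at least one listed symptom by 48 h, and add this to the closing list of comparisons. The chi-squared test already planned would apply. Keep opioid receipt, and any event attributed to an opioid, as a descriptive record.

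**Cost.** About one minute at each of four visits that already take place, one line on the case report form and one sentence in the Statistical Analysis Plan. No extra staff are needed.

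**Downside.** The new measure is all-cause. Recorded rates will be higher, and the opioid-caused difference is somewhat diluted: 4.8 instead of 6.0 points in the assumed case of 60% v 40% use, 20% background and 30% opioid effect. It answers a slightly different question from objective 3, so that objective should be worded to match.

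### Age and BMI are collected but have no role in the Timed Up and Go comparison; a pre-specified adjustment could gain precision at a cost of two degrees of freedom

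*Combined protocol and SAP*

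**What the plan says.** The Statistical Analysis Plan opens with "The age, gender, BMI, ASA status will be collected". It does not say what these four variables are for. The only test it names for numerical outcomes comes with a condition: "For normally distributed numerical variables the Student t test will be used to compare means". Categorical outcomes get a Chi-squared test. No covariate, regression model or stratification factor appears anywhere in the document.

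Design and Methods specifies the ambulation outcome: "Patients ability of early ambulation will be evaluated using Timed Up and Go (TUG) test at 24 and 48 hours after surgery". It is a continuous measure: "The time taken by a patient to perform this test will be calculated with a chronometer". No preoperative TUG is described. The same section ends by saying that "both groups of patients will be compared in terms of the extent of motor blockade postoperative pain control, ability of early ambulation", among other outcomes. Early ambulation is also in the stated aim, but not among the four numbered objectives.

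The sample size rests on a different outcome: "The variable for power calculation analysis is the difference in motor blockade between the groups of patients". It comes to 33 per group, and "However, due to possible missing data, 80 patients will be included in the study".

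**The concern.** In a randomised comparison of a continuous outcome, baseline variables that predict the outcome can be put in the model to take their share of the variance out of the error term. The SAP collects two continuous candidates, age and BMI, and then plans a comparison that ignores them. With no preoperative TUG described, the most obvious covariate is not available, which leaves these two as the continuous baseline measurements in hand.

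At stake is the width of the TUG confidence interval, and hence the power to see a difference in early ambulation. TUG has no power calculation of its own, so its precision is whatever the motor-blockade sample size happens to deliver. Validity is not in question, and no gain is claimed for motor blockade, pain scores or satisfaction.

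**Working it through.** **The plan's own figure.** The documents give no figure for TUG. The 33 per group is for motor blockade and cannot be confirmed, because no reference rate or SD is stated. For an absolute 30-point difference in proportions (pooled variance, two-sided 0.05, 90% power) the requirement runs from 28 per group (0% v 30%) to 57 (35% v 65%), with 33 arising at 3% v 33%. Read as a difference in means, 33 per group implies a standardised effect of (1.960 + 1.282) × √(2/33) = 0.80. Neither reading bears on TUG. The missing-data allowance is 1 − 66/80 = 17.5%.

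**Inputs from the documents.** 80 patients in two groups, 33 per group required, two-sided α of 0.05, two linear covariates (age, BMI). Equal allocation is assumed from the equal group sizes, giving n = 40 per group if all have TUG data and n = 33 if the whole allowance is lost.

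**Assumptions.** R², the share of within-group TUG variance explained by age and BMI, is set at 0, 0.05, 0.10, 0.20 and 0.30. The true difference is set at 0.5 or 0.65 SD. Errors are normal with equal variance on the chosen scale.

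**Formulas**, with N = 2n, k = 2, in SD units:

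- Unadjusted: variance 2/n, df = N − 2.
- Adjusted: variance (2/n) × (1 − R²) × [1 + k/(N − k − 3)], df = N − 2 − k.
- 95% CI half-width: t(0.975, df) × √variance.
- Power: noncentral t with noncentrality (difference)/√variance.

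**Price of two degrees of freedom.** The bracketed factor is 1 + 2/75 = 1.0267 at n = 40 and 1 + 2/61 = 1.0328 at n = 33. Residual df fall from 78 to 76, or from 64 to 62. On variance, break-even R² = 1 − 1/factor, which is 0.026 and 0.032. On interval width, which also counts the slightly larger t quantile, it is 0.027 and 0.033.

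**Worked case, n = 40.** Unadjusted half-width: 1.9908 × √0.05 = 0.445 SD. Adjusted at R² = 0.20: variance 0.05 × 0.80 × 1.0267 = 0.04107, half-width 1.9917 × √0.04107 = 0.404 SD, which is 9.3% narrower.

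| 40 per group | Unadjusted | R² = 0 | 0.05 | 0.10 | 0.20 | 0.30 |
|---|---|---|---|---|---|---|
| CI half-width (SD) | 0.445 | 0.451 | 0.440 | 0.428 | 0.404 | 0.378 |
| Change in width | – | +1.4% | −1.2% | −3.8% | −9.3% | −15.2% |
| Power, 0.5 SD | 59.8% | 58.7% | 60.9% | 63.2% | 68.3% | 74.0% |
| Power, 0.65 SD | 81.9% | 80.9% | 82.8% | 84.7% | 88.6% | 92.3% |

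| 33 per group | Unadjusted | R² = 0 | 0.05 | 0.10 | 0.20 | 0.30 |
|---|---|---|---|---|---|---|
| Change in width | – | +1.7% | −0.9% | −3.5% | −9.0% | −14.9% |
| Power, 0.5 SD | 51.6% | 50.3% | 52.3% | 54.5% | 59.5% | 65.2% |
| Power, 0.65 SD | 73.9% | 72.5% | 74.7% | 76.9% | 81.6% | 86.4% |

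**Simulation check** (20,000 trials per cell, 0.5 SD), adjusted v unadjusted power:

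- n = 40: 58.3% v 59.8% at R² = 0; 68.4% v 59.4% at R² = 0.20.
- n = 33: 50.4% v 51.8% at R² = 0; 58.9% v 51.2% at R² = 0.20.

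With no group difference, type I error was 4.7–5.3% adjusted and 4.7–5.2% unadjusted.

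**The case against.** The strongest reply is that nothing is broken. The unadjusted test is unbiased and holds its error rate, and recording age, gender, BMI and ASA status simply to describe the sample is ordinary practice. The SAP promises no adjusted analysis, so it contradicts nothing. This stands, and the point is accordingly an efficiency suggestion and not an error.

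The second reply is that the benefit depends on an R² that the documents do not give. Nothing in them links age or BMI to TUG time, and the four baseline variables are listed on equal terms. This also stands. The largest gain shown reflects only where the assumed grid stops, and at R² of 0.05 to 0.10 the interval narrows by just 1.2–3.8% at 40 per group. The choice has to be made under that uncertainty, with a maximum expected loss that is small and known. Age and BMI are preferred because they are continuous and cost one degree of freedom each; ASA I–III would cost two.

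Third, the t test applies only if TUG time passes the normality check, and no method is named if it fails. The unadjusted power figures therefore describe the plan only on a scale where the t test would be used. Suggesting log time also changes the effect measure from a difference to a ratio. Both remarks are fair. Log time is only an example; what matters is that one scale is chosen beforehand and used for both analyses.

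Fourth, some patients may be unable to do the test, and even 33 per group with TUG data is not assured. That is true, but it affects both analyses and adjustment does not resolve it.

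**Conclusion.** The point holds as something to consider. Age and BMI are collected, the planned TUG comparison makes no use of them, and including both as linear terms costs exactly two degrees of freedom. At an assumed 0.5 SD difference, the effect on power ranges from a loss of about 1 percentage point if they explain nothing to a gain of about 14 points at R² = 0.30. The documents do not locate the trial within that range.

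Confidence is medium: the reading of the plan and the arithmetic are secure, but R², the TUG difference, the completion counts and normal errors of equal variance are all assumed. Priority is modest, since ambulation is in the aim but is neither a numbered objective nor the outcome that sets the sample size.

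**What to change.** Before any outcome data are seen, add to the Statistical Analysis Plan:

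- TUG at 24 hours and at 48 hours will each be analysed by a linear model of group plus age and BMI as continuous terms.
- One scale is fixed in advance, for example log time with the group effect reported as a ratio, and the effect is given with a 95% CI.
- The unadjusted comparison on the same scale is kept as a sensitivity analysis.
- No other covariates enter, and neither the scale nor the standard error is chosen from the data.

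The cost is SAP wording, since both variables are already collected. If age and BMI explain none of the TUG variation, the variance of the group difference rises by about 2.7% at 40 per group (3.3% at 33). The handling of patients who cannot perform the test needs its own statement in the SAP.

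### Preoperative opioid use is not recorded at baseline although opioid need is compared between arms: a small, cheap gain in precision is missed, not a threat to validity

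*Combined protocol and SAP*

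**What the plan says.** Opioid need enters the plan in two places. Objectives, item 3 reads "To estimate the need for additional opioid analyses and their adverse effects" (the word printed as analyses evidently means analgesics). The closing sentence of Design and Methods then lists, among the outcomes on which the groups will be compared, "need for additional opioid analgesics, satisfaction rates over the time of clinical recovery".

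After surgery, opioids are available as "intramuscular boluses of pethidine 50 mg or morphine 10 mg without restriction and administered for moderate or severe pain". On recording, Design and Methods says "The requirement of additional analgesics and their adverse effects will be recorded", which covers the postoperative period. It does not say whether the outcome is yes/no, a number of boluses or a dose.

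Entry is defined by ASA "physical status I-III in preoperative assessment, aged 18-90 years, scheduled for primary total knee replacement surgery". No exclusion criteria are listed and opioid use is not mentioned. Allocation is described as "Preoperatively patients will be blindly randomized into one of two groups", with no stratification factor.

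The baseline sentence of the Statistical Analysis Plan is "The age, gender, BMI, ASA status will be collected". The tests named there are the Student t test for normally distributed numerical variables and the chi-squared test for categorical ones. Neither uses a covariate.

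**The concern.** A patient who already takes opioids before surgery can be expected to ask for more afterwards, particularly when rescue is given on demand. That is clinical reasoning; the documents give no figure for it. As written, the entry criteria do not keep such patients out, and none of the four baseline items stands in for prior use.

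Two things follow for this one outcome. The difference between users and non-users stays in the residual variance, so the comparison is less precise than it could be. And if prior users happen to fall mostly in one arm, the report cannot show it or adjust for it. The word additional also has no clear reference point for a patient whose usual intake is unknown.

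**Working it through.** The plan gives no figure for opioid need, so there is none to reproduce. Its sample size (33 per group, 80 enrolled) concerns motor blockade and is not at issue here.

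**Inputs**
- From the Statistical Analysis Plan: 80 patients. Equal allocation is assumed, so 40 per arm.
- Assumed, not in the documents: opioid need counted in boluses; non-users have mean 3 and SD 2; prior users need r = 2 times as much; their share q is 5%, 15% or 30% (4, 12 or 24 of 80 patients).

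**Step 1: ratio of unadjusted to adjusted standard error**

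Between-stratum variance: B = q(1-q)[(r-1)·3]², which is 9q(1-q) for r = 2. Adjustment removes B.

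Within-stratum variance: W = 4(1-q) + q·V, where V is the variance among users. Ratio = √[(W+B)/W]. It does not depend on the number of patients, and it ignores the small cost of estimating the covariate effect.

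Three choices of V:
- constant SD: V = 4
- variance proportional to the mean: V = 4r = 8
- SD proportional to the mean: V = 4r² = 16

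| q | B | V = 4 | V = 8 | V = 16 |
|---|---|---|---|---|
| 5% | 0.4275 | √(4.4275/4) = 1.05 | √(4.6275/4.2) = 1.05 | √(5.0275/4.6) = 1.05 |
| 15% | 1.1475 | √(5.1475/4) = 1.13 | √(5.7475/4.6) = 1.12 | √(6.9475/5.8) = 1.09 |
| 30% | 1.89 | √(5.89/4) = 1.21 | √(7.09/5.2) = 1.17 | √(9.49/7.6) = 1.12 |

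The standard error is therefore about 5%, 9-13% and 12-21% larger without adjustment.

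A more extreme case, r = 3 with q = 15%, has B = 0.1275·36 = 4.59. The ratios are √(8.59/4) = 1.47, √(9.79/5.2) = 1.37 and √(13.39/8.8) = 1.23. The result is sensitive to the spread assumed among users.

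**Step 2: chance imbalance at q = 15%, r = 2, constant SD**

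The SD of the between-arm difference in the share of users is √(0.15·0.85·2/40) = 0.080. Times 3 boluses, this moves the mean difference by 0.24 boluses per SD of imbalance.

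The adjusted SE is √(4·2/40) = 0.447 and the unadjusted SE is √(5.1475·2/40) = 0.507. Then √(0.507² - 0.447²) = 0.24. The imbalance figure is the extra standard error of Step 1 in other units.

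**Step 3: how often a visible imbalance would occur**

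Simulated with 40 per arm, the chance that the arms differ by at least 10 percentage points in prior users is 19%, 33% and 39% for shares of 10%, 20% and 30%. For at least 15 points it is 4%, 12% and 18%.

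**The case against.** The strongest case against is that nothing here is invalid. Prior use is fixed before randomisation and its variance is already inside the pooled SD of the planned t test, so the unadjusted test does not lose control of type I error. A reader might infer that the opioid comparison is biased; the documents do not support that. This objection stands and limits the point to precision and transparency.

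A reader might also take the wider standard error and the 0.24-bolus shift as two separate harms. Step 2 shows that they are one variance component. Nor should the 47% in the extreme case be taken as the likely loss: it needs threefold need together with no extra spread among users, and it falls to 23-37% if spread rises with the mean.

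The outcome also carries limited weight. The sample size is based on motor blockade. Objective 3 speaks of estimating need; the comparison between arms comes from the list closing Design and Methods.

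It would go too far to say that prior use could never be recovered. The protocol refers to a preoperative assessment, and medication history may be in that record. What can be said is that the plan commits neither to collecting it nor to using it.

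Finally, adding a covariate is a little more than it sounds, because the SAP contains no regression model and the scale of the outcome is not stated. This stands and is counted in the cost.

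**Conclusion.** The point holds as a minor, optional improvement. On the text, preoperative opioid use is neither collected nor addressed at entry, and no adjusted analysis is planned, although opioid need is an objective and a between-group comparison.

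Under the assumed twofold need, the avoidable widening of the standard error runs from about 5% to about 21% across shares of 5% to 30%. Everything in that range rests on assumed means, SDs and shares; if few users are enrolled the loss is small. The standard-error calculation applies to an amount of opioid and does not carry over directly to a yes/no outcome. The validity of the planned unadjusted test and the sample size are unaffected.

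**What to change.** 1. At enrolment, before the envelope is opened, record preoperative opioid use as none, occasional or daily, with drug and daily dose. Add it to the baseline list in the Statistical Analysis Plan and report it by arm.
2. State the scale of the opioid-need outcome, and pre-specify an adjusted comparison beside the unadjusted test. Use a linear or count model for an amount and a logistic model for yes/no.
3. Enter prior use as any versus none, or at three levels. A covariate for daily use alone would leave occasional users unadjusted and would not match the calculation above. With very few users (5% of 80 is 4 patients), any versus none is the workable coding.
4. Say in advance which of the two analyses is the main one. For a yes/no outcome, the adjusted odds ratio and the crude comparison estimate different quantities.

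The cost is one question on the case report form, one or two degrees of freedom and one regression model added to the SAP. Entry criteria and treatment do not change; whether to limit entry is a separate decision for the sponsor and is not needed for this fix.

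### The trial is sized on one motor-blockade comparison at two-sided 5%, but blockade is graded at four times, and no time point, summary or multiplicity rule says which comparison carries that 5%

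*Combined protocol and SAP*

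**What the plan says.** The power paragraph of the Statistical Analysis Plan rests on one quantity: "The variable for power calculation analysis is the difference in motor blockade between the groups of patients". The effect is given as "The difference in motor blockade of 30% would be clinically significant", without saying whether 30% is an absolute difference in the proportion blocked, a relative change or a difference in means. No control rate or SD is given. The size follows: "for a power of 90% and a 2-tailed α error of 0.05, a sample size of 33 patients per group would be required". Enrolment is then raised: "due to possible missing data, 80 patients will be included in the study".

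In the Study Protocol, under Design and Methods, the same variable is measured four times: "The extent of motor blockade will be evaluated at 3, 6, 24, 48 hours after surgery". The instrument is an ordered scale: "The possible leg motion at 3, 6, 24 and 48 hours postoperatively will be assessed with Bromage scale grades". The closing sentence of that section says that "both groups of patients will be compared in terms of the extent of motor blockade postoperative pain control", and ends its list of outcomes with "satisfaction rates over the time of clinical recovery".

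The analysis paragraph names two tests: Student's t for normally distributed numerical variables and chi-squared for categorical ones. It sets one significance threshold of 0.05. Nowhere is there a primary outcome or time point, a summary over time, a repeated-measures method, a test hierarchy or an adjustment.

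**The concern.** A power statement at 90% and two-sided 5% describes one test. Here there are four candidate tests of the sizing variable, and the plan does not say which of them, or which combination, the two percentages belong to. Each named test compares one value per patient, so the natural execution is one p-value per time point, each read against 0.05.

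The choice of time point could then be made after the results are seen. Blinding of the participant and outcome assessor does not guard against this, because the selection happens at analysis. A claim that the blocks differ in motor blockade, resting on whichever time reached 0.05, would not carry the 5% error that the sample-size statement implies. The variable concerned is the first objective and the only one used to justify the size of the trial.

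A smaller and conditional matter is the test. None is assigned to motor blockade by name. Of the two named, chi-squared is the one that fits Bromage grades, and applied to ungrouped grades it ignores their order. This does not arise if the 30% means a proportion blocked (yes/no), but then the grade cut-off is missing.

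**Working it through.** **Inputs from the documents:** 90% power, two-sided 0.05, 33 per group, 80 enrolled, a 30% difference, four assessment times, threshold 0.05. **Assumed, because not given:** correlation between time points, block rates, SD and grade distribution.

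**1. The plan's own figure.** With (1.960 + 1.2816)² = 10.507:
- Two means, standardised effect 0.8 (30% with an SD of 37.5%): n = 2 × 10.507 / 0.8² = 32.8, so 33 per group (34 by the exact t test).
- Two proportions, 3% v 33%, pooled variance under the null: n = [1.960√(2 × 0.18 × 0.82) + 1.2816√(0.03 × 0.97 + 0.33 × 0.67)]² / 0.30² = (1.065 + 0.641)² / 0.09 = 32.3, so 33.
- Other 30-point differences need from 28 (0% v 30%) to 57 (35% v 65%) per group.

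So 33 is attainable but not uniquely reproducible. Every route to it is a single test on one value per patient.

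**2. Any-of-four error, four informative tests.** If independent, 1 − 0.95⁴ = 0.185. For equicorrelated normal statistics, the chance that at least one exceeds 1.96 in absolute value is:

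| Correlation | 0 | 0.3 | 0.5 | 0.7 | 0.8 | 0.9 |
|---|---|---|---|---|---|---|
| At least one false positive | 18.5% | 17.4% | about 15.5% | 13.0% | 11.4% | 9.4% |

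**3. Only 3 and 6 hours informative** (nobody still blocked later). If independent, 1 − 0.95² = 0.0975. At correlation 0.7 it is about 8.4%, and at 0.9 about 7%.

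**4. Simulated null data, 33 or 40 per group, latent correlation 0.3 to 0.9, assumed block profiles.**
- Four grades, chi-squared: 12-19% if block persists; 10-11% with 10% blocked at 24 h and none at 48 h; about 9% with 3% and 1%.
- Yes/no, uncorrected chi-squared: about 13-21% if block persists, 10-12% with 3% and 1% blocked at 24 and 48 h. At this size the uncorrected test can itself run slightly above 5%.
- Yes/no with continuity correction, which the plan does not mention: about 4-11%, near 5% if block has gone by 24 h. The upper end depends on the profile; with half the patients blocked at all four times it can be somewhat exceeded.

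**5. Power cost of restricting the claim.** Take an effect with 90% power in one test at 33 per group.
- Any-of-four, effect at one time: 1 − 0.10 × 0.95³ = 91.4% if independent, rising to 93.9% at correlation 0.9.
- Any-of-four, effect at two times: 1 − 0.10² × 0.95² = 99.1% if independent, falling to about 96% at correlation 0.9.
- Bonferroni over four (0.0125): Φ(√10.507 − 2.498) = Φ(0.744) = 77% at 33; Φ(√(10.507 × 40/33) − 2.498) = Φ(1.071) = 86% at 40.

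**6. Test choice (conditional).** The same effect spread over more degrees of freedom gives 83.5% (2 df) or 78.4% (3 df) at 33 per group, and 90.2% or 86.3% at 40. For an assumed 3.4% v 33.4% blocked, with all block in one grade, chi-squared has 94% at 33. Mann-Whitney for a 0.8 SD shift cut into four grades gives 77-84% at 33 and 84-91% at 40, depending on the assumed baseline grades. Figures at 40 assume equal allocation and all 80 evaluable.

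**The case against.** The strongest reply is that the plan contains no any-of-four rule. It speaks of one difference in motor blockade and of comparison across recovery. A single value per patient, such as the worst grade, would fit the named tests and give one 5% test. Four separate time-specific conclusions would each carry 5%. This stands: the inflation is conditional on how the claim is made. A reader might infer that the plan declares success on any one time point, so that its true error is 9-19%. The documents do not support that, because they state no such rule.

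It also stands that 9% is not a floor. High correlation and absence of late block can occur together, and a continuity-corrected yes/no test can show no inflation at all.

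The reply does not supply what is missing. The reference to recovery over time names no summary and no longitudinal method, and worst grade is only one possibility among several. Because the plan does not choose, an any-of-four claim stays open.

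Two other inferences should be resisted. One is that 33 per group is wrong: it can be reached under plausible inputs, and what is missing is the inputs. The other is that power is only about 78%: that holds only for an ungrouped chi-squared on 3 df, and it disappears if the 30% is a proportion blocked.

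**Conclusion.** The concern holds in conditional form. The comparison to which the 90% power and two-sided 5% belong is not identified, and nothing prevents a motor-blockade claim from resting on any of four unadjusted tests. If that happens, the false-positive chance is about 9-19% with four informative tests (correlation 0.9 to 0) and about 7-10% with two. For a continuity-corrected yes/no endpoint it is about 4-11% under the profiles assumed. So it exceeds 5% in most scenarios, but not in all. The ranges rest on assumed correlations and block profiles.

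This is more than missing detail, since it concerns the error rate of the conclusion for which the trial was sized. It should be corrected, and the correction is cheap. The choice of test for ordered grades is secondary and depends on what the 30% means.

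**What to change.** Before unblinding, amend the Statistical Analysis Plan as follows.

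- Name one primary motor-blockade comparison at two-sided 0.05: either a single time point, or one pre-specified summary or repeated-measures comparison over the four times.
- Label the remaining time-point comparisons secondary, or adjust them (for example by Holm).
- If Bromage grades are compared, use an ordered-category test (Mann-Whitney or linear trend) instead of an ungrouped chi-squared. If the 30% is a proportion blocked, state the grade cut-off, keep chi-squared and say whether it is continuity-corrected.
- State the rates, or the mean difference and SD, behind 33, and restate the power for the chosen test. Do not carry 90% at 33 per group over to Mann-Whitney.
- Keep 80 enrolled.

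This costs text only: no added patients, visits or data. The downside is that a difference seen only outside the primary comparison can no longer be the main result. Power is also lower than under the unadjusted any-of-four rule. For an effect giving 90% in a single test at 33 per group, it is 90% against 91-94% if the effect is at one time, or against 96-99% if at two. The power at 40 per group is not a safe substitute, because the 14 patients beyond 66 (14/80 = 17.5%) are there to cover missing data.
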